7.1.2. Analytical Methodology

Plasma concentrations of OLP-1002 will be determined using validated analytical procedures. Specifics of the analytical methods will be provided in separate documents.

7.2. Pharmacodynamic Assessments

Capsaicin intradermal test will be performed for subjects in Groups A2, A4, and A6. Each subject will be tested at a pre-screening visit before being tested twice during the study (1 predose and 1 postdose).

7.2.1. Capsaicin-evoked Pain Model

The capsaicin model will be conducted by intradermal injection of capsaicin (100 μg in 100 μL of sterile saline containing 8% [w/w] Tween 80) into the skin of the anterior aspect of the forearm, midway between the elbow and the wrist. The bleb area (wheal) will be a sign of local plasma extravasation. An assessment of the pain intensity related to capsaicin injection will be estimated by repeated use of a VAS from injection to 5 minutes post-injection or until the pain intensity returned to zero. The AUC, E_{max} , and tE_{max} will be calculated and reported using dedicated software.

7.2.2. Secondary Hyperalgesia

The area of secondary hyperalgesia will be quantified with a 60-g weighted von Frey hair, by stimulating along 8 linear paths (4 vectors crossing at the location of the injection site) arranged vertically and horizontally around the stimulation site in 5-mm steps (starting approximately 6 cm away from the injection site). The area of secondary hyperalgesia will be evaluated at 5 and 30 minutes post-capsaicin injection.

7.3. Safety and Tolerability Assessments

Safety and tolerability assessments will be conducted at the times indicated in the Schedule of Assessments ([Appendix 6](#)). Timepoints may be adjusted based on an ongoing review of the data, and additional assessments may be conducted if deemed necessary by the Investigator or designee.

7.3.1. Adverse Events

Adverse event definitions, assignment of severity and causality, and procedures for reporting SAEs are detailed in [Appendix 1](#).

The condition of each subject will be monitored from the time of signing the ICF to final discharge from the study. Subjects will be observed for any signs or symptoms and asked

about their condition by open questioning, such as “How have you been feeling since you were last asked?”, at least once each day while resident at the study site and at each study visit. Subjects will also be encouraged to spontaneously report AEs occurring at any other time during the study.

Any AEs and remedial action required will be recorded in the subject’s source data. The nature, time of onset, duration, and severity will be documented, together with an Investigator’s (or designee’s) opinion of the relationship to study drug.

Adverse events recorded during the course of the study will be followed up, where possible, until resolution or until the unresolved AEs are judged by the Investigator (or designee) to have stabilized. This will be completed at the Investigator’s (or designee’s) discretion.

7.3.2. Clinical Laboratory Evaluations

Blood and urine samples will be collected for clinical laboratory evaluations (including clinical chemistry, hematology, urinalysis, and serology) at the times indicated in the Schedule of Assessments in [Appendix 6](#). Clinical laboratory evaluations are listed in [Appendix 2](#). Additional clinical laboratory evaluations will be performed at other times if judged to be clinically appropriate or if the ongoing review of the data suggests a more detailed assessment of clinical laboratory safety evaluations is required.

Subjects will be asked to provide urine samples for drugs of abuse screen and cotinine test, and will undergo an alcohol breath test at the times indicated in the Schedule of Assessments in [Appendix 6](#). For all female subjects, a follicle-stimulating hormone (FSH) test and pregnancy test will be performed at the times indicated in the Schedule of Assessments in [Appendix 6](#).

An Investigator (or designee) will perform a clinical assessment of all clinical laboratory data.

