3.6. Dose Escalation

In Part A, doses will be administered in an escalating manner following satisfactory review by the Sponsor and Investigator of the safety, and tolerability data up to Day 10 (216 hours postdose) from groups that received lower doses of OLP-1002. For escalation to doses > 12 µg, PK data up to Day 7 (144 hours postdose) will also be reviewed. All available safety, tolerability, and PK data from previous groups will be reviewed prior to dose escalation.

In Part B, doses will be administered in an escalating manner following satisfactory review of safety, tolerability, and PK data up to Day 22 (216 hours post-final dose) from groups that received lower doses of OLP-1002. Doses may be reduced and may be lower than the starting dose. Available safety, tolerability, and PK data from all previous groups will be reviewed prior to dose escalation.

Dose escalation in Part A will only occur if data from a minimum of 4 subjects (Groups A1, A3, A5, A7, and A8) or 6 subjects (Groups A2, A4, and A6) have been reviewed from the previous lower dose group, such that data from a minimum of 3 or 4 subjects, respectively, who have received OLP-1002 will be used to make the dose-escalation decision. Dose escalation in Part B will only occur if data from a minimum of 6 subjects have been reviewed from the previous lower dose group, such that data from a minimum of 4 subjects who have received OLP-1002 will be used to make the dose-escalation decision.

The justification for this is as follows:

- The study drug is of a known pharmacological class for which the on-target effects in humans are well characterized. Based upon nonclinical data, no clinically important off-target effects are expected within the proposed dose range.

- A minimum of 3 subjects receiving the active drug is considered sufficient to characterize the safety profile for OLP-1002.

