Appendix 3: Total Blood Volume

The following blood volumes will be withdrawn for each subject.

Part A

	Volume per blood sample (mL)	Maximum number of blood samples	Total amount of blood (mL)
Pharmacokinetic analysis	4	19	76
Clinical laboratory evaluations (excluding serology)	7.5	6	45
Serology	3.5	1	3.5
Total:			124.5

Part B

	Volume per blood sample (mL)	Maximum number of blood samples	Total amount of blood (mL)
Pharmacokinetic analysis	4	29	116
Clinical laboratory evaluations (excluding serology)	7.5	10	75
Serology	3.5	1	3.5
Total:			194.5

If extra blood samples are required, the maximum blood volume to be withdrawn per subject during the study will not exceed that donated during a standard blood donation (approximately 500 mL).

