^a A positive urine pregnancy test result will be confirmed with a serum pregnancy test.

^b All times are relative to dosing with OLP-1002.

^c Continuous ECG recording may begin at approximately 25 hours before dosing to allow for checks to be completed prior to the first extraction timepoint and will continue for 24 hours postdose, ie, until after the last timepoint for ECG extraction (24 hours postdose). At timepoints for ECG extractions, subjects will be supinely resting for a total of 15 minutes (10-minute supine rest period, 5-minute extraction). Data will be archived for potential future analysis and will not be available for review during the study.

^d Pharmacodynamic assessment groups only.

^e PK analysis in Part A will initially only be conducted for groups receiving $\geq 12 \mu\text{g}$ OLP-1002, with retrospective analyses of samples from lower dose groups occurring in the event of PK data being quantifiable at doses $\geq 12 \mu\text{g}$ and if supported by bioanalytical stability data.

Study Plan – Part B (Multiple Dose)

	Screening	Day -1	Days 1-15	Day 18 (± 2 days)	Day 22 (± 2 days)	Day 25 (± 2 days)	Day 29 (± 2 days)	Poststudy (Day 57 ± 2 days)
Inclusion/exclusion criteria	X							
Demographic data	X							
Medical history	X							
Urine drugs of abuse screen	X	X						
Alcohol breath test	X	X						
Cotinine test	X	X						
Serology	X							
Hormone panel	X							
Urine pregnancy test ^a	X	X			X		X	X
Informed consent	X							
Study residency:								
Check-in		X						
Check-out			Day 15 (48 hours postdose)					
Non-residential visit	X			X	X	X	X	X
Study drug administration:			Days 1, 4, 7, 10, and 13					
Safety and tolerability:								
Adverse event recording	X	X	Ongoing	X	X	X	X	X
Concomitant medication recording	X	X	Ongoing	X	X	X	X	X
Supine blood pressure, pulse rate, respiratory rate, and body temperature	X		Day 1: predose, 1, 2, 4 and 8 hours postdose Day 2, Day 4 (postdose), Day 5, Day 7 (postdose), Day 9, Day 10 (postdose), Day 12, Day 13: predose, 1, 2, 4 and 8 hours postdose, and Day 15	X	X	X	X	X

	Screening	Day -1	Days 1-15	Day 18	Day 22	Day 25	Day 29	Poststudy (Day 57 ± 2 days)
Heat pain threshold test (heat pain threshold and heat pain tolerance)	X		Day 1 and Day 13: predose, 1, 2, 4, 8, 24 hours postdose					
Supine 12-lead ECG	X		Day 1: predose and 4 hours postdose Day 4: predose and 4 hours postdose Day 7: predose and 4 hours postdose Day 10: predose and 4 hours postdose Day 13: predose and 4 hours postdose Day 15		X		X	X

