Appendix 6 - Schedule of assessments Part B

Clinical chemistry, haematology, and urinalysis for Days 1-15 previously read:

Days 2, 4, 7, ~~10,13~~

Clinical chemistry, haematology, and urinalysis for Days 1-15 now reads:

Days 2, 5, 9, 12, 17

PK blood sampling for Days 1-15 previously read:

Day 1 and Day ~~15~~: Pre dose, 0.5, 1, 1.5, 2, 3, 4, 6, 8 and 12 hours post dose
Days 4, 8, ~~11, 15~~ Predose

PK blood sampling for Days 1-15 now reads:

Day 1 and Day **13**: Pre dose, 0.5, 1, 1.5, 2, 3, 4, 6, 8 and 12 hours post dose
Days 4, 7, **10** Predose

Day 15

Protocol Amendment 1 (Version 2; 02 October 2018)

This amendment has been generated following the non-acceptance of the original protocol (version 1) by the Medicines and Healthcare products Regulatory Agency (MHRA) on 20 September 2018. All changes made have been in response to comments provided by the MHRA.

The primary changes in this amendment are:

1. Inclusion of PK sampling in Parts A and B:
 - PK objective and exploratory endpoints added (Section 2).

- Discussion of PK included Section 3.4.
 - PK stopping criteria added to Section 3.7.
 - PK assessments included in Section 7.1.
 - PK population and analysis (Section 8.2.1).
 - Blood volumes updated to include samples for PK assessments (Appendix 3).
2. Exclusion and stopping criteria updated
 - Women who are pregnant or breastfeeding have been excluded from the study (Section 4.2).
 - Liver function tests, tachycardia, and hypertension stopping criteria have been updated (Section 3.7 and Section 4.4).
 - Stopping criteria for SAEs and serious AEs have been added (Section 3.7 and Section 4.4).
 3. Safety, tolerability, and PK data up to Day 22 in Part B will be reviewed prior to dose escalation (Section 3.1.2).
 4. Sentinel dosing included in Part B (Section 3.1.2).
 5. It has been specified that the maximum dose for additional groups will not exceed 20 µg (Section 3.5.3).

Minor changes:

1. Additional clinical laboratory evaluations have been included on Day 14 in Part A.
2. The definition of the Safety population has been updated to include all subjects who receive OLP-1002.
3. Typographical errors and formatting errors were corrected, as necessary.

A detailed summary of changes is presented below. For each section, deleted text is shown in ~~strike through~~, and new text is shown in **bold**:

Section 1.6

Previously read:

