3.1.2. Part B

Part B will comprise a multiple-dose, sequential-group study. Overall, 24 subjects will be studied in 3 groups (Groups B1 to B3), with each group consisting of 8 subjects. Up to 3 additional groups (24 subjects in total) may be included for further assessment of safety and tolerability ([Section 3.3](#)).

Potential subjects will be screened to assess their eligibility to enter the study within 28 days prior to the first dose administration. Each subject will participate in 1 treatment period only and reside at the CRU from Day -1 until Day 15.

All subjects will return for non-residential visits on Days 18 (± 2 days), 22 (± 2 days), 25 (± 2 days), and 29 (± 2 days), and for a poststudy visit on Day 57 (± 2 days).

[figure not shown]
In each of Groups B1 to B3, 6 subjects will receive OLP-1002 and 2 subjects will receive placebo. For all subjects, a single subcutaneous dose will be administered on Days 1, 4, 7, 10, and 13. Prior to each dosing occasion a physician will review the available safety and tolerability data from each subject to confirm it is acceptable to continue dosing. The dosing frequency in Part B may be changed following review of data from groups in Part A ([Section 3.4](#)).

Sentinel dosing will only occur in Part B at dose levels where exposure to OLP-1002 at steady state is predicted to exceed exposures that have been shown to be safe and well tolerated in earlier groups in Parts A or B. In the event of sentinel dosing, 2 subjects (1 active, 1 placebo) will be dosed at least 4 days prior to the remaining 6 subjects (5 active: 1 placebo). Safety data for the sentinel subjects from at least 2 additional doses will be reviewed prior to dosing the remaining subjects (i.e. sentinel subjects' safety data after doses 1 and 2 will be reviewed prior to the remaining subjects receiving dose 1). In addition, safety data from each subject will be reviewed by a physician prior to each dose to approve continued dosing.

Doses will be administered in an escalating manner following satisfactory review of safety, tolerability, and PK data up to Day 22 (216 hours post-final dose) from the lower dose levels. Part B may start after a review of the safety, tolerability, and available PK for Groups A1 to A6. The total daily dose administered will not exceed the highest single dose given in Part A.

An overview of the study design is shown in [Figure 2](#).

Figure 2: Study Schematic (Part B)

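### The Part B laboratory draw listed for Day 17 falls after the Day 15 check-out and is assigned to no visit, so the only sample planned between the last dose and Day 22 is not guaranteed

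*Protocol*

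**What the plan says.** Section 7.3.2 sets no laboratory times itself and defers to the Schedule of Assessments in Appendix 6: "Blood and urine samples will be collected for clinical laboratory evaluations (including clinical chemistry, hematology, urinalysis, and serology) at the times indicated in the". The Part B study plan there (version 2.2) gives the following:

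- Dosing is on "Days 1, 4, 7, 10, and 13".
- Check-out is at "Day 15 (48 hours postdose").
- In the column for Days 1 to 15, the chemistry, haematology and urinalysis row reads Days 2, 5, 9, 12, 17. It has further marks at Screening, Day -1, Day 22, Day 29 and Day 57, and none at Day 18 or Day 25.

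Section 3.1.2 agrees on attendance after discharge: "All subjects will return for non-residential visits on Days 18 (± 2 days), 22 (± 2 days"), followed by Days 25, 29 and 57. The pages at hand show that section only in version 2.1 and earlier. The Amendment 3 summary lists no change to it, and the version 2.2 table has the same visits.

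Day 17 entered with Amendment 2, under the line "Clinical chemistry, haematology, and urinalysis for Days 1-15 now reads". It replaced a list that ended on Day 13, and it remains in the current table.

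On the use of the data, Section 3.6 says: "In Part B, doses will be administered in an escalating manner following satisfactory review of safety, tolerability, and PK data up to Day 22".

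**The concern.** Day 17 cannot belong to the column it is printed in, lies two days after discharge and is not a named visit day. The next visit, Day 18, has an empty laboratory cell. Staff following the table column by column would draw blood on Day 12 and next on Day 22.

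That interval contains the fifth and last dose and, on the protocol's own half-life, the highest accumulated exposure. The incidence of laboratory abnormalities is a primary safety endpoint (Section 2.2.1). Liver tests feed the escalation stopping rule (Section 3.7) and individual withdrawal (Section 4.4). If the draw is missed, a subject leaves the unit on Day 15 with the last laboratory check taken before the final dose, and a change that rises and settles before Day 22 would not be seen. A missed draw could affect all 24 planned Part B subjects, and up to 48 if the three optional groups are added.

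**Working it through.** **Is the draw intended?** Appendix 3 allows 10 Part B samples under "Clinical laboratory evaluations (excluding serology") at 7.5 mL each. Counting the schedule: Screening, Day -1, Days 2, 5, 9, 12 and 17, then Days 22, 29 and 57, makes 10. 10 × 7.5 = 75 mL, and 116 + 75 + 3.5 = 194.5 mL, the stated total. Without Day 17 the count is 9 and the volume 67.5 mL. The draw was therefore planned and budgeted.

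**Which day was probably meant?** The laboratory days fall between doses. In the vital-signs row, which also covers dosing days, the non-dosing days are 2, 5, 9, 12 and 15. The laboratory row matches except for its last entry. Within the same column the ECG, injection-site and PK rows also end at Day 15. In Part A, laboratory tests are taken at 48 hours postdose, which is check-out. This points to Day 15 but does not prove it.

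**Can it be taken on Day 17?** The first return visit is Day 18 ± 2, that is Days 16 to 20. Day 17 is a permitted attendance day, but the column for that visit calls for no laboratory sample.

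**Gap if the draw is missed.**
- Day 12 to Day 22: 10 days. With Day 22 ± 2: 20 − 12 = 8 to 24 − 12 = 12 days.
- First value after the last dose: (22 − 13) × 24 = 216 h; range (20 − 13) × 24 = 168 h to (24 − 13) × 24 = 264 h.

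**Gap after Day 12 if it is taken.**
- Day 15: 3 days, 48 h after the last dose.
- Day 18 ± 2: 4 to 8 days, nominally 120 h after the last dose.

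**Where exposure peaks.** Inputs are five doses at 0, 72, 144, 216 and 288 h and the 180 h human half-life of Section 3.5.2, with the 84 h monkey value as a check. Assume one compartment and instantaneous absorption. The level relative to one dose is the sum of 0.5^((t − x)/half-life) over the doses x given by time t = 24 × (day − 1).

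Just after the Day 13 dose, with 180 h: 1 + 0.758 + 0.574 + 0.435 + 0.330 = 3.10.

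| Day | 180 h | 84 h |
|---|---|---|
| 12 | 2.30 | 1.36 |
| 13, after dose | 3.10 | 2.12 |
| 15 | 2.57 | 1.43 |
| 17 | 2.14 | 0.96 |
| 18 | 1.95 | 0.79 |
| 22 | 1.35 | 0.36 |

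The peak follows the Day 13 dose under both half-lives. With 180 h, 2.57/3.10 = 83% of it remains on Day 15, 1.95/3.10 = 63% on Day 18 and 1.35/3.10 = 44% on Day 22.

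**The case against.** The best defence is that the sample is unassigned rather than omitted. It is listed, it is counted in the blood volume, and a site that notices the mismatch has two obvious places to take it: check-out or the Day 18 visit. Section 7.3 allows timepoints to be adjusted on ongoing review, and Section 7.3.2 allows extra tests when judged clinically appropriate. Exposure is also not unsampled near its peak: with 180 h the level after the fourth dose is 2.77, or 89% of the maximum, and the Day 12 sample follows it. The rat kidney findings in Section 1.4 were judged non-adverse and persisted through recovery at the top dose, so a change of that kind would still show on Day 22.

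Much of this stands, and it limits the point. A reader might infer that nobody is at the unit on Day 17, that the data are lost, or that escalation would go ahead with no laboratory value after the final dose. The documents support none of these. The Day 18 window includes Day 17, the draw is planned, and the Day 22 panel is marked and falls within the escalation data cut-off.

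What the defence does not supply is a guarantee. The provisions for extra tests depend on clinical judgement or data review, and a silent transaminase or renal change prompts neither. As the table stands, the sample requires a visit held a day early and a draw that the visit's column does not request.

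**Conclusion.** The point holds as an internal inconsistency in the Part B table of Appendix 6. Section 7.3.2 contains no error; it only makes that table binding. One of the 10 planned Part B laboratory samples, the only one between the last dose and Day 22, is tied to no visit. If it is missed, the gap is nominally 10 days (8 to 12), and the first value after the final dose comes at about 216 h (168 to 264 h), when about 44% of the peak level remains. That percentage rests on the 180 h half-life and a one-compartment model; the timing figures rest on the schedule alone.

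It does not follow that the sample will be missed, or that the escalation review would lack any laboratory data after the fifth dose. The harm is conditional and the toxicology summary gives no specific signal for it. The correction is still worth making before Part B dosing, because the sample serves a primary safety endpoint and the liver stopping rule near peak accumulation, and securing it costs almost nothing.

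**What to change.** In the Part B laboratory row of Appendix 6, change Day 17 to Day 15. This is check-out, 48 h after the last dose. It matches the last in-house entry of the vital-signs, ECG, injection-site and PK rows, gives a laboratory result at discharge and shortens the gap after Day 12 to 3 days. If a later sample is preferred, delete Day 17 from that column and mark the draw at Day 18 (± 2 days), which leaves a gap of 4 to 8 days.

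The cost is one schedule entry. Appendix 3 stays at 10 samples and 75 mL, with no added blood or visit. Amendments 2 and 3 changed laboratory timepoints as non-substantial amendments, and the same route should serve here.

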7.3.3. Vital Signs

Supine blood pressure, supine pulse rate, respiratory rate, and body temperature will be assessed at the times indicated in the Schedule of Assessments in [Appendix 6](#). Vital signs may also be performed at other times if judged to be clinically appropriate or if the ongoing review of the data suggests a more detailed assessment of vital signs is required.

Day 1 predose blood pressure, pulse rate, and respiratory rate will be measured in triplicate at approximately 2-minute intervals. The median value will be used as the baseline value in the data analysis. All subsequent measurements will be performed singly and repeated once if outside the relevant clinical reference ranges.

Subjects must be supine for at least 5 minutes before blood pressure, pulse rate, and respiratory rate measurements.

7.3.4. Electrocardiogram

7.3.4.1. 12-lead Electrocardiogram

Resting 12-lead ECGs will be recorded after the subject has been supine and at rest for at least 5 minutes at the times indicated in the Schedule of Assessments in [Appendix 6](#). Single 12-lead ECGs will be repeated once if either of the following criteria apply:

- QTcF value > 500 msec
- QTcF change from the mean baseline (Day 1 predose) is > 60 msec.

Additional 12-lead ECGs may be performed at other times if judged to be clinically appropriate or if the ongoing review of the data suggests a more detailed assessment of ECGs is required. The Investigator (or designee) will perform a clinical assessment of each 12-lead ECG.

Day 1 predose 12-lead ECGs will be measured in triplicate at approximately 2-minute intervals. The mean value will be used as the baseline value in the data analysis. All subsequent measurements will be performed singly and repeated once if outside the relevant clinical reference ranges.

7.3.4.2. Continuous (24-hour) Electrocardiogram

At the times indicated in the Schedule of Assessments ([Appendix 6](#)), continuous (24-hour) ECGs will be performed.

Subjects will be supine for at least 10 minutes before the extraction timepoint and for 5 minutes from the start of each extraction timepoint. Each extraction will last for 5 minutes. Environmental distractions (eg, television, playing games, radio, conversation) should be avoided during the pre-ECG time window.

Continuous 24-hour ECGs are not planned for Part B of the study but may be implemented if any clinically significant findings are identified in the data from Part A.

